11. SAMPLE SIZE CALCULATION

Assuming a risk of CRC of 1% at 10 years for patients with low risk adenoma and of 2% for patients with high-risk adenomas at baseline and using a non-inferiority hypothesis with an equivalence interval of 0.5% for patients with low risk adenomas and 0.7% for patients with high risk adenomas, we need to include 6,783 individuals in each arm of the EPoS I trial, and 6,852 in each arm of the EPoS II trial. That supposes a total of 13,566 individuals randomized in the EPoS I and 13,704 in the EPoS II trial (with a power of 90% and a one-sided alpha of 0.05, see table).

The table shows power scenarios for 80% and 90% power for EPoS I and II, respectively.

Table 2: Power Analysis for EPoS I and EPoS II, based on non-inferiority tests of two independent proportions.

	Power	10 year CRC incidence (proportion)		Group size	Total sample size
		P1 proportion	P2 proportion		
EPoS I	80%	0.01	0.015	4897	9794
EPoS I	90%	0.01	0.015	6783	13566
EPoS II	80%	0.02	0.027	4947	9894
EPoS II	90%	0.02	0.027	6852	13704

P1 is the control group (shorter surveillance intervals), P2 is the intervention group (longer surveillance intervals).

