11. STATISTICAL ANALYSIS PLAN

Participants are followed for the primary endpoint (incidence of CRC), until death/incidence of CRC or end of follow-up, whichever happens first. All randomised participants are followed up through national or regional registries, regardless of whether they continue in the study or not. The primary analytic approach of the trial will follow the intention-to-treat (ITT) principle. We will compare the ~~average rate~~

~~of differences for~~ each endpoint between the intervention groups by calculating risk differences and log-rank test ~~fitting a Cox proportional hazards model~~. The limit for the statistical significance will be established in 0.05 and 95% confidence intervals will be calculated. If the distribution of any baseline characteristics is found to be imbalanced between the arms, we will conduct a sensitivity analysis in which those characteristics will be included as covariates in the model.

We will also do analyses to estimate the causal effect that would have been observed if all individuals in the intervention arms had been compliant. We will refer to these analyses as “adherence-adjusted” analyses. We will use two different analytic approaches to obtain “adherence-adjusted” estimates: instrumental variables methods and inverse probability weighting. For comparability, we will translate the estimates from both approaches into a common metric: adjusted (CRC-free) survival curves. To implement instrumental variables methods (with the indicator for treatment arm as the instrument), we will use g-estimation of nested structural models. To implement inverse probability weighted estimation, we will estimate the weights and the parameters of a marginal structural Cox model. The estimation of inverse probability weights in one intervention arm requires the measurement of variables that jointly predict compliance with the baseline intervention and the endpoint. These variables include age, sex, baseline findings, physical activity, family history of colorectal cancer, smoking status, use of aspirin, NSAIDs, and hormone replacement therapy (9).

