- Thirdly, colonoscopy is costly and resource demanding. As a corollary, resources saved by less frequent surveillance of adenoma patients might convey greater public health benefit if used for other purposes in the health care system.
- Fourthly, the level of inferiority considered acceptable need and should not be the same in EPoS I as in EPoS II. Instead, we argue that a slightly higher absolute difference (inferiority) in cumulative incidence of colorectal cancer would be justifiable in EPoS II. This argument is based on the fact that in EPoS II, subjects randomized to less intense surveillance are spared one or probably two colonoscopies during a 5-year period compared with currently applied guidelines. In contrast, subjects enrolled in the EPoS I trial would be spared only one colonoscopy over a 10-year period.

In conclusion, based on the arguments outlined above, and acknowledging that any defined level of inferiority can be considered arbitrary, we have accepted an equivalence level of 0.5% in absolute colorectal cancer incidence in EPoS I, and of 0.7% in EPoS II. This implies that the null hypothesis of non-inferiority would be

rejected only if the upper limit of the 95% confidence interval for the absolute difference in cumulative incidence of colorectal cancer after ten years of follow-up exceeds 0.5% in EPoS I and 0.7% in EPoS II.

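### Both trials are sized at one-sided alpha 0.05 but judged on a 95% confidence interval, so the stated 90% power is about 83%

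*Protocol*

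**What the plan says.** The sample size section gives the design inputs: "Assuming a risk of CRC of 1% at 10 years for patients with low risk adenoma and of 2% for patients with high-risk adenomas", with "an equivalence interval of 0.5% for patients with low risk adenomas and 0.7% for patients with high risk adenomas". From these it concludes that "we need to include 6,783 individuals in each arm of the EPoS I trial, and 6,852 in each arm of the EPoS II trial", "with a power of 90% and a one-sided alpha of 0.05". Table 2 adds the sizes for 80% power: 4,897 and 4,947 per arm.

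The decision rule is in section 11.1. Its null hypothesis is "rejected only if the upper limit of the 95% confidence interval for the absolute difference in cumulative incidence of colorectal cancer after ten years" lies above 0.5% in EPoS I or 0.7% in EPoS II.

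The statistical analysis section says only this about error rates: "The limit for the statistical significance will be established in 0.05 and 95% confidence intervals will be calculated". It does not mention sidedness. Nothing in the protocol says that the interval is one-sided, or that a 90% interval will be used for the non-inferiority decision.

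**The concern.** Comparing the upper limit of a two-sided 95% interval with a margin is a one-sided test at 0.025. The sizing allows 0.05. One primary test therefore has two error rates, and the power in Table 2 belongs to the one that section 11.1 does not apply.

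Two things are at stake. First, the advertised power is too high for the rule as written. Second, the protocol gives no agreed reading of a result that falls between the two rules, with the upper limit of the 90% interval below the margin and that of the 95% interval above it. Such a result would pass by the sample size section and fail by section 11.1. After ten years of follow-up and 13,566 + 13,704 = 27,270 randomised patients, the conclusion could depend on which section is consulted.

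**Working it through.** **Inputs.** From the sample size section: control risk p = 0.01 (EPoS I) and 0.02 (EPoS II); margin m = 0.005 and 0.007; one-sided alpha 0.05; power 80% or 90%. From the randomisation section: 1:1 allocation. The true difference used for sizing is not stated. It is taken as zero because this reproduces the published sizes. The P2 column of Table 2 is P1 plus the margin, not the alternative at which power was computed.

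**Formula.** Per arm, n = (z_alpha + z_power)² × 2p(1−p) / m².

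The factor 2p(1−p)/m² is 0.0198/0.000025 = 792 in EPoS I and 0.0392/0.000049 = 800 in EPoS II.

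**Step 1: reproduce the plan.** With z_alpha = 1.645, the squared sum is 8.564 for 90% power and 6.183 for 80%. With z_alpha = 1.960 it is 10.507 and 7.849.

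| Trial, power | Table 2 | n at one-sided 0.05 | n at one-sided 0.025 |
|---|---|---|---|
| EPoS I, 80% | 4,897 | 4,896.6 | 6,216.3 |
| EPoS I, 90% | 6,783 | 6,782.6 | 8,321.9 |
| EPoS II, 80% | 4,947 | 4,946.0 | 6,279.1 |
| EPoS II, 90% | 6,852 | 6,851.1 | 8,405.9 |

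Rounded up, the one-sided 0.05 column matches all four entries (the EPoS II 80% value is slightly above 4,946). The 0.025 column matches none. Calculations using P1 and P2 as the true risks do not match either: at 90% power and one-sided 0.05 with unpooled variance they give 8,453 and 8,017.

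**Step 2: power under the section 11.1 rule.** Power = Φ(m / √(2p(1−p)/n) − z_alpha), with z_alpha = 1.960.

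- EPoS I, n = 6,783: 0.005/√(0.0198/6,783) = 2.926; Φ(2.926 − 1.960) = 83.3%.
- EPoS II, n = 6,852: 0.007/√(0.0392/6,852) = 2.927; Φ(2.927 − 1.960) = 83.3%.
- EPoS I, n = 4,897, and EPoS II, n = 4,947: Φ(2.487 − 1.960) = 70.1% in each.

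A simulation of 1,000,000 trials per study, using the simple (Wald) 95% interval and equal true risks, gave 83.3% in both. The Farrington-Manning score test gave 82.2% (EPoS I) and 82.8% (EPoS II).

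**Step 3: size of the gap.** The chance of missing non-inferiority when the strategies are identical is 100 − 83.3 = 16.7%, about 1 in 6. A result that passes one rule and fails the other then occurs in 90.0 − 83.3 = 6.7% of trials. Restoring 90% under the 95% interval would take 8,322 and 8,406 per arm (16,644 and 16,812 in total); 10.507/8.564 = 1.227, or 22.7% more.

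**The case against.** The strongest reply is that the 83% depends on reading the interval as two-sided. Neither section 11.1 nor the analysis section states sidedness. The only place that does is the sample size section, which says one-sided, and only the upper limit is used. If a one-sided 95% upper bound was meant, power stays at 90%. An analysis plan that is not at hand might define the interval.

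That dependency is real and should be stated. But the text gives no support for the one-sided reading. The protocol uses the ordinary term for the interval, and the one 95% interval it reports, from the Danish trial in the background section, has two limits. Even if a one-sided bound was intended, section 11.1 would still need rewording. The protocol itself fixes both values, so this is not a detail left to a later document.

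A second reply is that the error is on the safe side. The 95% rule is stricter than planned, so the risk of wrongly declaring non-inferiority falls, and 83% still exceeds the 80% scenario that the protocol tabulates. This is correct. The harm is an overstated power and an unsettled decision rule, not a raised false-positive rate.

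A third point is that any single power figure is conditional. Section 11.1 itself expects a slightly higher incidence with less frequent surveillance. If the true excess were 0.1 percentage point (an illustrative assumption), power under the 95% interval would be about 63% in EPoS I and 70% in EPoS II. This also stands. It means that 83% is itself a favourable figure, and that the zero-difference assumption belongs beside it.

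**Conclusion.** The concern holds. The sizing and the decision rule use different error rates, and every power in Table 2 is overstated for the rule in section 11.1: 83.3% instead of 90%, and 70.1% instead of 80%, in both trials. These figures assume a two-sided 95% interval, the protocol's own control risks and margins, and a true difference of zero, which is also what the protocol's sizes assume.

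Section 11.1 also labels the hypotheses the wrong way round, treating non-inferiority as the null. That is a separate fault. The cut-off is the same either way, so the figures here do not change.

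**What to change.** Choose one error rate and use it in the sample size section, Table 2, the analysis section and section 11.1.

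- **Preferred:** keep the comparison of the 95% upper limit with the margin and say that the interval is two-sided. Restate the sizing as one-sided alpha 0.025, with power of 83% at 6,783 and 6,852 per arm and 70% at 4,897 and 4,947. State beside these figures that they assume a true difference of zero.
- **If one-sided 0.05 is really intended:** change section 11.1 and the analysis section so that non-inferiority is judged on the upper limit of a two-sided 90% interval. The 90% and 80% in Table 2 then stand.

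Under either option, correct the statement of the null hypothesis when section 11.1 is edited, and settle the choice before outcome data are compared between arms. The cost is protocol wording and, under the first option, new power figures in Table 2 and a less favourable headline. Margins, conduct and patient numbers are unchanged.

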11.1 Power rationale and Ethical considerations

Because removal of precursor lesions is assumed to prevent development of invasive cancer, it is implausible that less intense colonoscopic surveillance following adenoma removal would entail a lower cumulative incidence of colorectal cancer than more frequent surveillance. Such an outcome would, however, arise if the preventive effect of more frequent surveillance (with removal of incident adenomas) is outweighed by overdiagnosis of invasive cancer. A similar, or even identical, cumulative incidence of colorectal cancer following more or less frequent surveillance is theoretically possible, notably if the average progression time from a detectable precursor lesion (adenoma) to invasive cancer are longer than the different surveillance intervals applied in the EPoS trials. However, trials designed to document equivalence would require unrealistically large sample sizes and are therefore unlikely to ever be undertaken.

We considered as the most plausible outcome of the EPoS trials a slightly, perhaps only marginally, higher cumulative incidence of colorectal cancer with less than with more frequent colonoscopic surveillance. As a corollary, our two studies named EPoS I and EPoS II are both designed as non-inferiority randomized trials.

There are several reasons why trials designed to test this hypothesis are considered ethically justifiable:

- Firstly, colonoscopy carries risks, chiefly caused by bleeding or perforation of the colon. Although such complications are rare, notably in high quality settings, they are severe and sometimes life threatening. Hence, complications might substantially counteract the possible survival benefit of more intense surveillance which, in absolute terms (number of lives saved per colonoscopy) is small anyway.
- Secondly, screening to detect precursor lesions and invasive cancer may entail overdiagnosis and overtreatment of lesions that would never have progressed to a lethal stage during the individual's remaining lifetime. The probability of overdiagnosis is likely to be positively correlated with the number of surveillance colonoscopies. Although the extent of overdiagnosis is poorly quantified for colonoscopic screening, it is substantial for other, more established, screening tools such as PAP-smear for cervical cancer, mammography for breast cancer and prostate-specific antigen (PSA) for prostate cancer.
- Thirdly, colonoscopy is costly and resource demanding. As a corollary, resources saved by less frequent surveillance of adenoma patients might convey greater public health benefit if used for other purposes in the health care system.
- Fourthly, the level of inferiority considered acceptable need and should not be the same in EPoS I as in EPoS II. Instead, we argue that a slightly higher absolute difference (inferiority) in cumulative incidence of colorectal cancer would be justifiable in EPoS II. This argument is based on the fact that in EPoS II, subjects randomized to less intense surveillance are spared one or probably two colonoscopies during a 5-year period compared with currently applied guidelines. In contrast, subjects enrolled in the EPoS I trial would be spared only one colonoscopy over a 10-year period.

In conclusion, based on the arguments outlined above, and acknowledging that any defined level of inferiority can be considered arbitrary, we have accepted an equivalence level of 0.5% in absolute colorectal cancer incidence in EPoS I, and of 0.7% in EPoS II. This implies that the null hypothesis of non-inferiority would be

rejected only if the upper limit of the 95% confidence interval for the absolute difference in cumulative incidence of colorectal cancer after ten years of follow-up exceeds 0.5% in EPoS I and 0.7% in EPoS II.

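### Section 11.1 states the non-inferiority hypotheses the wrong way round, so the conclusion drawn when the upper confidence limit crosses the margin is mislabelled

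*Protocol*

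**What the plan says.** The last paragraph of Protocol Section 11.1 sets the only decision rule in the protocol that uses the margin. It begins "This implies that the null hypothesis of non-inferiority would be" and goes on: "rejected only if the upper limit of the 95% confidence interval for the absolute difference in cumulative incidence of colorectal cancer after ten years". The cut-off is met when that limit "exceeds 0.5% in EPoS I and 0.7% in EPoS II".

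Section 11 (Sample size calculation) describes the design as "using a non-inferiority hypothesis with an equivalence interval of 0.5% for patients with low risk adenomas", and as 0.7% for high-risk adenomas. The 90% power sizes are given "with a power of 90% and a one-sided alpha of 0.05". Table 2 is headed as a non-inferiority test of two independent proportions, with P1 the shorter and P2 the longer interval. Section 11.1 also says that both randomized studies are designed as non-inferiority trials.

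Section 11 (Statistical analysis plan) gives risk differences, a log-rank test, a 0.05 significance limit and 95% confidence intervals. It states no hypotheses and no margin, so it does not correct Section 11.1.

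**The concern.** In a non-inferiority test the null is that the new strategy is worse by at least the margin, and non-inferiority is what the data must establish. Section 11.1 reverses this. Two things follow if it is read as written.

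- **Upper limit above the margin.** The text rejects non-inferiority, and rejecting that null formally means accepting inferiority. Such a limit shows only that inferiority by the margin has not been excluded. Evidence of inferiority beyond the margin needs the lower limit to exceed the margin.
- **Upper limit below the margin.** The text yields only a failure to reject. The positive conclusion that the trials are designed to reach, that the longer interval is non-inferior, has no formal basis in the sentence.

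This matters because Section 11.1 itself regards a small excess of cancer with longer intervals as the most plausible outcome. In that region the interval will often span the margin.

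**Working it through.** **1. Which null does the sample size use?**

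Inputs from Section 11: p = 0.01 and margin m = 0.005 (EPoS I); p = 0.02 and m = 0.007 (EPoS II); one-sided alpha 0.05; power 80% or 90%. Take H0: P2 − P1 ≥ m, with a true difference of 0:

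n per arm = (z_alpha + z_power)² × 2p(1 − p) / m²

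- The variance factor is 2 × 0.0099 / 0.000025 = 792 for EPoS I and 2 × 0.0196 / 0.000049 = 800 for EPoS II.
- At 90% power, (1.6449 + 1.2816)² ≈ 8.564. At 80% power, (1.6449 + 0.8416)² ≈ 6.183.

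| Trial | Power | Protocol | Recomputed |
|---|---|---|---|
| EPoS I | 80% | 4,897 | 4,897 |
| EPoS I | 90% | 6,783 | 6,783 |
| EPoS II | 80% | 4,947 | 4,947 |
| EPoS II | 90% | 6,852 | 6,852 |

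All four agree. A one-sided superiority comparison of P1 with P2 at alpha 0.05 and 90% power would give 8,455 and 8,020, which do not match. The planned test therefore has inferiority by at least the margin as its null, the reverse of Section 11.1.

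**2. How often does the upper 95% limit exceed the margin?**

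Normal approximation at 6,783 and 6,852 per arm, with control risk as assumed in Section 11 and true excess d:

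SE = √{[p(1 − p) + (p + d)(1 − p − d)] / n}

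P(upper limit > m) = 1 − Φ[(m − d)/SE − 1.96]

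P(lower limit > m) = 1 − Φ[(m − d)/SE + 1.96]

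Worked case, EPoS I with d = 0: SE = √(2 × 0.0099 / 6,783) = 0.00171; 0.005/SE = 2.927; 2.927 − 1.960 = 0.967; the tail is 0.167.

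| True excess | EPoS I: upper > m | EPoS I: lower > m | EPoS II: upper > m | EPoS II: lower > m |
|---|---|---|---|---|
| 0 | 16.7% | <0.001% | 16.7% | <0.001% |
| 0.2 points | 61.2% | 0.014% | 46.8% | 0.003% |
| equal to m | 97.5% | 2.5% | 97.5% | 2.5% |

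Percentages are of all trials. With no true difference, 14.2 of the 16.7 points also have a lower limit at or below zero. With a 0.2-point excess, inside both margins, the upper limit often passes the margin, while the lower limit does so in under 0.02% of trials. These results are almost all inconclusive about inferiority beyond the margin.

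**3. Which hypothesis does the cut-off fit?**

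At a true difference equal to m, the upper limit falls below m in 2.5% of trials. That is the error rate of a proper test of H0: difference ≥ m using a 95% interval. Treated instead as a test of a null of non-inferiority, the same cut-off would reject in 97.5% of trials at the edge of that null. The cut-off belongs with the conventional null; the label attached to it is wrong.

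**The case against.** The strongest reply is that this is a slip of terminology. The comparison of upper limit with margin is the standard one, the sample size uses the right null, and Sections 11 and 11.1 both call the design non-inferiority. Non-inferiority survives in the same data sets under either wording. All of this stands, and it limits the point to the hypothesis statement and the conclusion attached to it.

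Three stronger readings are tempting, and the protocol does not support them.

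- **That an inconclusive result will be reported as proof of inferiority.** The protocol does not say how such a result would be reported. The text also says only if, which strictly is a necessary condition, although it supplies no other.
- **That the 17%, 61% and 47% are errors created by the wording.** They are the chances of not showing non-inferiority with a 95% interval, and they stay the same after correction. Only the label changes.
- **That the alpha and power control a different decision.** They relate to the same comparison of upper limit with margin. What does not match is the level: a 95% interval corresponds to one-sided 0.025, whereas Section 11 uses one-sided 0.05. That is a separate matter. It explains why the figure at zero difference is 16.7% and not the planned 10%.

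A separate statistical analysis plan, not at hand, might set out the full interpretation. It would still conflict with a protocol sentence that is wrong as it stands.

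**Conclusion.** The point holds as an error in the stated hypotheses for the primary endpoint of EPoS I and EPoS II. Section 11.1 contradicts the test behind Table 2, and nothing else in the protocol puts it right. Its practical reach is the interpretation of an interval that spans the margin, together with the formal standing of a favourable result. It does not change the cut-off, the group sizes or the frequency of any outcome.

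The situation is not rare: about one trial in six with no true difference, and roughly half or more with a 0.2-point excess, would have an upper limit above the margin. These frequencies assume the control risks in Section 11, full recruitment at 90% power, simple proportions without loss to follow-up, and a normal approximation.

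**What to change.** Replace the last sentence of Section 11.1 with wording such as:

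> H0: 10-year incidence (longer interval) minus 10-year incidence (shorter interval) is at least 0.5 percentage points in EPoS I (0.7 in EPoS II). H1: the difference is smaller. H0 is rejected and non-inferiority concluded if the upper limit of the two-sided confidence interval, at the stated level, is below the margin. If the upper limit is at or above the margin, non-inferiority is not shown. Inferiority beyond the margin is concluded only if the lower limit exceeds the margin.

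State the confidence level in that paragraph and make it consistent with the alpha in Section 11. A two-sided 90% interval matches the one-sided 0.05 used for the sample size. If the 95% interval is kept, the matching alpha is one-sided 0.025, and power at the stated sizes is about 83% (100% − 16.7%).

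The restatement costs one paragraph in an amendment and leaves the group sizes unchanged. It should be made before endpoint data are seen, because a later correction to the primary decision rule would look post hoc.
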